5.3.2. Per Protocol Population

The PP Population will include randomized participants who are considered to be sufficiently compliant with the Protocol. It is defined for the supportive analysis for primary efficacy endpoint in the DBVC period. Participants with important Protocol deviations, as defined below, will be excluded from the PP Population.

In general, the following are important Protocol deviations that may have an essential impact on the primary analysis:

- Missing primary endpoint data (ie, WI-NRS score at Week 12) for any reason, including early withdrawal from the DBVC period.
- Study cream application compliance, as defined in Section 6.5, is below 60%.

In addition, Protocol deviations related to inclusion/exclusion criteria, discontinuation criteria, and use of prohibited medications will be reviewed. Decisions as to whether any of these deviations warrant exclusion from the PP Population will be made before the unblinding of the study.

5.3.3. Safety Population

The Safety Population will include all participants who applied ruxolitinib 1.5% cream or vehicle cream at least once. Treatment groups for this population will be determined according to the actual treatment the participant applied on Day 1 regardless of assigned treatment group.

The Safety Population will be used for safety summaries in the DBVC period.

5.3.3.1. Open-Label Extension Safety Population

The OLE Safety Population will include all participants who applied ruxolitinib 1.5% cream at least once during the OLE period.

All safety analyses conducted specifically for the OLE period will use the OLE Safety Population.

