6. STUDY TREATMENT

6.1. Study Treatments Administered

Ruxolitinib 1.5% cream or matching vehicle cream will be applied as a thin film BID on each pruriginous lesion and the surrounding area of the lesion (~ 1 cm), with applications at least 8 hours apart in the morning and in the evening at least 1 hour before bedtime.

On Day 1 and at Week 12 (if applicable), the participant will apply a thin film of study cream to the treatment area under the supervision of site staff. The treatment area is defined as the area affected by pruriginous lesions plus an \sim 1 cm area surrounding each lesion. During the DBVC period, all other applications of study cream will be applied by the participant to the treatment area identified at baseline. The total BSA treatment area must be \leq 20%. Participants should not apply the application of study cream at home prior to clinic visits at Week 2, Week 12/EOT1, and Week 52/EOT2 (see Section 8.5).

At the baseline visit, an estimate of the %BSA treatment area will be used by the IRT system to calculate the number of tubes of study cream to be dispensed. All areas identified at baseline should continue to be treated through the end of the DBVC period (Week 12) unless the participant meets criteria for stopping study cream (see Section 6.5.2). If there are new pruriginous lesions to be treated, after consultation with the investigator, study cream should be applied to these lesions in addition to the areas treated at baseline (total BSA treatment area must be $\leq 20\%$), and the percentage of BSA to be treated will be recalculated and increased. This new estimate will be entered into the IRT system to calculate the number of tubes of study cream to be dispensed.

During the OLE period starting at the Week 12 visit, pruriginous lesions will be evaluated by the investigator to confirm whether the participant still requires continuation of therapy (ie, IGA-CPG-S score ≥ 1 and/or the presence of itching related to PN). Participants with an IGA-CPG-S score of 0 may continue or restart therapy if there is itch associated with underlying PN, or they can otherwise (re)enter the observation/no-treatment cycle (ie, IGA score of 0 and WI-NRS score of 0). At Week 12, the IRT system will dispense a prespecified number of tubes according to the assessment of total BSA treatment area.

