3. STUDY DESIGN

This is a Phase 3, multicenter, randomized, DBVC, parallel-group study in adults with PN (IGA-CPG-S score of ≥ 2 ; ≥ 6 pruriginous lesions on ≥ 2 different body areas; and PN-related WI-NRS score ≥ 7). The study will consist of a 12-week DBVC period followed by a 40-week OLE period.

[figure not shown]
Participants will be screened for up to 4 weeks prior to the first application of study cream. Approximately 180 eligible participants will be randomized 1:1 to either ruxolitinib 1.5% cream or vehicle cream. Participants will be stratified by baseline IGA-CPG-S score ($2 \text{ or } \ge 3$) and geographic region (North America or outside of North America). Participants will apply either ruxolitinib 1.5% cream BID or vehicle cream BID through Week 12 to all pruriginous lesions identified at baseline.

At Week 12, participants who have completed 12 weeks of treatment with no safety concerns will enter the 40-week OLE period. Participants randomized to vehicle cream BID at baseline will be crossed over to ruxolitinib 1.5% cream BID and participants randomized to ruxolitinib 1.5% cream BID at baseline will remain on ruxolitinib 1.5% cream BID through Week 52. Participants will enter the 30-day safety follow-up period after the EOT/ET visit.

During the OLE period, starting at the Week 12 visit, pruriginous lesions will be evaluated by the investigator to confirm whether the participant still requires continuation of therapy (ie, IGA-CPG-S score ≥ 1 and/or the presence of itching related to PN). Participants with an IGA-CPG-S score of 0 may continue or restart therapy if there is itch associated with underlying PN, or they can otherwise (re)enter the observation/no-treatment cycle (ie, IGA-CPG-S score of 0 and WI-NRS score of 0).

The study design schema is shown in Figure 1.

Figure 1: Study Design Schema

RUX = ruxolitinib.

The primary analysis will occur after the primary database lock, when all participants have completed or discontinued from the DBVC period. The final analysis will occur when all participants have completed or withdrawn from the study.

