5.3. Analysis Populations

5.3.1. Intent-to-Treat Population

All participants who are randomized will constitute the ITT Population. Treatment groups for this population will be defined according to the treatment assignment at the time of randomization regardless of the actual study cream the participant might apply during their participation in the DBVC period.

The ITT Population will be used for the summary of demographics, baseline characteristics, participant disposition, medical history, prior and concomitant medications, and analyses of all efficacy data, unless otherwise specified.

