6.2. Disposition of Participants

The number and percentage of participants who were randomized, who were treated, who completed the DBVC period, who discontinued treatment during the DBVC period with a primary reason for discontinuation, and who withdrew from the study during the DBVC period with a primary reason for withdrawal will be summarized for the ITT Population.

The number and percentage of participants who completed the OLE period, who discontinued treatment during the OLE period with a primary reason for discontinuation, and who withdrew from the study during the OLE period with a primary reason for withdrawal will be summarized for the OLE Safety Population.

The number of participants enrolled by country and site will also be provided by treatment group.

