2.1.3.2	Summary and Analysis of By-Visit WI-NRS Score in the OLE Period	OLE Safety	
2.1.4	Summary and Analysis of Time to ≥ 2-Point Improvement in Daily WI-NRS Score From Baseline During the DBVC Period	ITT (baseline daily WI-NRS score ≥ 2)	
2.1.5	Summary and Analysis of Time to ≥ 4-Point Improvement in Daily WI-NRS Score From Baseline During the DBVC Period	ITT (baseline daily WI-NRS score ≥ 4)	
2.1.3	Summary and Analysis of Daily WI-NRS Score From Baseline to Day 14	ITT	
2.2.1	Summary and Analysis of Participants Achieving Overall-TS in the DBVC Period	ITT	
2.2.2	Summary and Analysis of Participants Achieving Overall-TS From Day 1 to Week 52	ITT	
2.3.1	Summary and Analysis of Participants Achieving IGA-CPG-S-TS in the DBVC Period	ITT	
2.3.2	Summary and Analysis of Participants Achieving IGA-CPG-S-TS From Day to Week 52	ITT	
2.4.1	Summary and Analysis of Participants Achieving IGA-CPG-A-TS in the DBVC Period	ITT	
2.4.2	Summary and Analysis of Participants Achieving IGA-CPG-A-TS From Day 1 to Week 52	ITT	
2.5.1	Summary and Analysis of By-Visit Skin Pain NRS Score in the DBVC Period	ITT	
2.5.2	Summary and Analysis of By-Visit Skin Pain NRS Score in the OLE Period	OLE Safety	
2.5.3	Summary and Analysis of Participants Achieving ≥ 2-Point Improvement in By-Visit Skin Pain NRS Score From Baseline During the DBVC Period	ITT (baseline Skin Pain NRS score ≥ 2)	
2.5.4	Summary and Analysis of Participants Achieving ≥ 2-Point Improvement in By-Visit Skin Pain NRS Score From Baseline During the OLE Period	OLE Safety (baseline Skin Pain NRS score ≥ 2)	
2.6.1	Summary and Analysis of Participants Achieving > 75% Healed Lesions From PAS in the DBVC Period	ITT	
2.6.2	Summary and Analysis of Participants Achieving > 75% Healed Lesions From PAS in the OLE Period	OLE Safety	
2.7.1.1	Summary and Analysis of DLQI Total and Subscale Scores in the DBVC Period	ITT	
2.7.1.2	Summary and Analysis of DLQI Total and Subscale Scores in the OLE Period	OLE Safety	
2.7.2	Summary and Analysis of Participants Achieving ≥ 4-Point Improvement in DLQI Total Score in the DBVC Period	ITT (baseline DLQI total score ≥ 4)	
2.8.1.1	Summary and Analysis of EQ VAS Score in the DBVC Period	ITT	
2.8.1.2	Summary and Analysis of EQ VAS Score in the OLE Period	OLE Safety	
2.8.2.1	Summary of Participants in Each Category of Each Dimension of the EQ-5D-5L in the DBVC Period	ITT	

Table No.	Title	Population	Standard

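### OLE disposition and seven OLE-period efficacy tables use the OLE Safety Population, which can omit participants who enter the OLE clear and itch-free and never reapply cream

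*SAP*

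**What the plan says.** **The population.** SAP 5.3.3.1 defines it by exposure: "The OLE Safety Population will include all participants who applied ruxolitinib 1.5% cream at least once during the OLE period". It gives the set a safety purpose: "All safety analyses conducted specifically for the OLE period will use the OLE Safety Population".

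**Its other uses.** SAP 6.2 applies the same set to OLE disposition, including participants "who withdrew from the study during the OLE period with a primary reason for withdrawal will be summarized for the OLE Safety Population"; Table 1.1.2.2 follows. In Appendix A the population column reads OLE Safety for Table 2.1.3.2 ("Summary and Analysis of By-Visit WI-NRS Score in the OLE Period"), and also for 2.5.2 and 2.5.4 (Skin Pain NRS score and improvement of at least 2 points), 2.6.2 (PAS, more than 75% healed), 2.7.1.2 (DLQI), 2.8.1.2 (EQ VAS) and 2.8.2.2 (EQ-5D-5L dimensions).

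**The efficacy default.** SAP 5.3.1 assigns ITT to "analyses of all efficacy data, unless otherwise specified". Appendix A lists ITT for the responder tables running to Week 52: 2.1.1.2 (WI-NRS4), 2.2.2 (Overall-TS), 2.3.2 (IGA-CPG-S-TS) and 2.4.2 (IGA-CPG-A-TS).

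**Treatment in the OLE.** From Week 12 the investigator judges whether therapy is still needed. SAP section 3 says participants with IGA-CPG-S 0 may continue or restart for itch, "or they can otherwise (re)enter the observation/no-treatment cycle (ie, IGA-CPG-S score of 0 and WI-NRS score of 0"). Protocol 6.1 has nearly the same sentence.

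**The concern.** Being in the OLE and applying cream in the OLE are different things. A participant who reaches Week 12 with no lesions and no itch can enter in a no-treatment cycle, and then joins the OLE Safety Population only if lesions or itch return and cream is restarted. Someone who enters and withdraws before applying any cream is left out as well. For adverse events this is harmless, since there is no OLE exposure to attribute them to. For efficacy and disposition, the denominator is selected on something that happens after entry.

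Protocol 2.2.1 gives the OLE the purpose of assessing safety and efficacy under intermittent dosing. Participants who stay well off treatment are direct evidence on that, and they are the ones at risk of omission from the listed tables. If clearance at Week 12 is more common after 12 weeks of active cream than after vehicle, the two OLE sequences would also be selected to different degrees. OLE completion and withdrawal counts need not reconcile with the number who continued from the double-blind period.

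**Working it through.** The plan states no figure that depends on this choice, so there is none to reproduce. The check has two parts.

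**1. Can an OLE entrant have no OLE application?**

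- *Yes, on one reading.* Protocol 6.1 and SAP section 3 provide for a no-treatment cycle beginning as early as the Week 12 visit. Protocol 6.1 qualifies the supervised Week 12 application as applying only where relevant, without saying when that is.
- *No, on another reading.* Protocol Table 3 marks a supervised application at Week 12, and its note exempts only those not continuing into the OLE. Protocol 8.1.4 has cream applied after the Week 12 blood draws. Protocol 4.1 says all participants apply cream during the OLE.

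The documents do not settle this. On the second reading nobody who enters is lost.

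**2. How large could the effect be?** Let f be the share of OLE entrants who never apply cream in the OLE and r the response rate in all entrants. If every omitted participant is a responder, the OLE Safety table shows

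(r − f) / (1 − f).

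For example, r = 50% and f = 5% give 0.45 / 0.95 = 47.4%. The documents do not give f; the range is assumed. Each cell shows the displayed rate, with the understatement in percentage points in brackets.

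| f | r = 30% | r = 50% | r = 70% |
|---|---|---|---|
| 0% | 30.0% (0) | 50.0% (0) | 70.0% (0) |
| 2% | 28.6% (1.4) | 49.0% (1.0) | 69.4% (0.6) |
| 5% | 26.3% (3.7) | 47.4% (2.6) | 68.4% (1.6) |
| 10% | 22.2% (7.8) | 44.4% (5.6) | 66.7% (3.3) |
| 20% | 12.5% (17.5) | 37.5% (12.5) | 62.5% (7.5) |

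Among the responder tables in the public list, this applies only to 2.5.4 (Skin Pain) and 2.6.2 (PAS).

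For the mean WI-NRS score in Table 2.1.3.2, suppose omitted participants score 0 and the rest average 3.0. The table shows 3.0; the mean over all entrants is 3.0 × (1 − f) = 2.94, 2.85, 2.70 and 2.40 for f = 2%, 5%, 10% and 20%.

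*Unequal selection.* With r = 50% in both sequences, f = 10% after ruxolitinib and f = 2% after vehicle, the displayed rates are 0.40 / 0.90 = 44.4% and 0.48 / 0.98 = 49.0%. That is a gap of about 4.5 points where none exists.

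*Early withdrawals.* Let g be the share who withdraw before applying and would count as nonresponders if kept. The displayed rate becomes (r − f) / (1 − f − g). With r = 50% and f = g = 2%, it is 0.48 / 0.96 = 50.0%, so the two omissions cancel. With g larger than f at r = 50%, the table would overstate response.

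**The case against.** The strongest reply is that the main durable-response results are safe. A reader might infer that open-label efficacy is summarised solely in participants who applied cream, and hence that durable response is understated. Appendix A does not support that: WI-NRS4, Overall-TS, IGA-CPG-S-TS and IGA-CPG-A-TS to Week 52 are all on ITT, so a participant who stays clear off treatment is not excluded from any of them. This objection stands and limits the point to the tables named above.

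Second, the mechanism may be empty. If everyone who continues applies cream in clinic at Week 12, as the Table 3 note can be read, f is zero. This also stands, as a condition on the finding.

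Third, the group is narrow. It needs complete clearance, zero itch, no clinic application and no restart over 40 weeks, although Protocol 6.1 allows restart at IGA-CPG-S 1 or more or any PN-related itch. Clear and itch-free participants would ordinarily also meet Overall-TS, which Protocol Table 12 plans at 30% on ruxolitinib and 10% on vehicle. The share who are clear and then never retreat should therefore lie well below those figures, and the 20% row above is an extreme.

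Fourth, a reader might call the plan self-contradictory for using ITT in some displays and OLE Safety in others. That is too strong: the ITT default allows exceptions, Appendix A makes them table by table, and displays over different periods may have different denominators. What remains is that no reason is visible. The text of SAP 7.6 and 7.7 is absent from the public copy and might contain one. Appendix A also calls its lists guidelines.

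Finally, the sentence defining the OLE Safety Population is correct for safety. The issue lies in its reuse in SAP 6.2 and Appendix A.

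**Conclusion.** The mismatch holds and is easy to verify: OLE disposition and seven OLE-period efficacy tables rest on a set conditioned on treatment after entry. It can omit participants who enter clear and never reapply, and those who withdraw before applying.

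Its size is unknown. It is zero if every entrant applies cream at Week 12. If all omitted participants are responders, f of 2% to 10% and true rates of 30% to 70% give an understatement of 0.6 to 7.8 points in the two affected responder tables. The direction is not guaranteed once early withdrawals are counted.

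The Week 52 ITT responder tables and the primary and key secondary tests, which use ITT in the double-blind period, are untouched. This is a cheap improvement to secondary OLE summaries and does not threaten the trial's conclusions.

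**What to change.** 1. Add to SAP 5.3 an entered-the-OLE set: all participants who completed Week 12 and continued, whether or not cream was applied, grouped by randomised arm. SAP 5.2 already presents efficacy by the group assigned at study entry.
2. Use it for Tables 2.1.3.2, 2.5.2, 2.5.4, 2.6.2, 2.7.1.2, 2.8.1.2 and 2.8.2.2, and for OLE disposition (SAP 6.2, Table 1.1.2.2). Keep the baseline Skin Pain restriction in 2.5.4.
3. Keep the OLE Safety Population for adverse events, laboratory values, vital signs and exposure.
4. Reconcile Protocol 6.1 with the Table 3 note on whether a participant who enters the OLE in a no-treatment cycle applies cream in clinic at Week 12. Report how many entrants had no OLE application.
5. Reconcile the diary period. The Protocol's schedule of activities runs the WI-NRS diary to the last application of cream, whereas Protocol 8.2.1 runs it to Week 52 or ET. Under the former, untreated participants would lack diary scores whichever population is used.

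The cost is one definition, one flag and relabelled tables. No new collection is needed for PAS, DLQI or EQ-5D-5L, which Table 4 schedules at OLE visits without regard to treatment status; for the diary scores this depends on item 5. The downside is that OLE efficacy and safety denominators may differ slightly, which a footnote can explain.

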5.3.4. Pharmacokinetic-Evaluable Population

The PK-Evaluable Population will include participants who applied ruxolitinib 1.5% cream at least once and provided at least 1 postbaseline blood sample for PK analysis. The study pharmacokineticist will review data listings of participant application and sample records to identify participants to be excluded from the analysis.

5.3.5. Pharmacodynamic-Evaluable Population

The PD-Evaluable Population will include participants who applied study cream at least once and provided a baseline PD sample and at least 1 postbaseline PD sample for analysis. The study translational scientist will review data listings of participant application and sample records to identify participants to be excluded from the analysis.

5.3.6. Pharmacokinetic/Pharmacodynamic Evaluable Population

The PK/PD-Evaluable Population will include all participants who are in both the PK-Evaluable and PD-Evaluable Populations, as well as participants who are PD-evaluable while receiving vehicle cream during the DBVC period.

6. BASELINE, EXPOSURE, AND DISPOSITION

Appendix A provides a list of data displays. Sample data displays are included in a separate document.

6.1. Demographics, Baseline Characteristics, and Disease History

6.1.1. Demographics and Baseline Characteristics

The following demographics and baseline characteristics will be summarized by treatment group and overall for the ITT Population in the DBVC period and for the OLE Safety Population in the OLE period: age, sex, race, ethnicity, weight, height, and BMI.

6.1.2. Baseline Disease Characteristics

For the ITT Population, the baseline disease characteristics will be summarized and analyzed by treatment group and will include but not be limited to the following:

- Disease duration (months)
- Prior history of atopic medical conditions (atopic dermatitis, asthma, allergic rhinitis, allergic conjunctivitis, food allergy, drug allergy, urticaria, anaphylaxis, and other)
- PN family history (yes/no)
- Skin type based on Fitzpatrick Scale
- PN-related skin infection requiring antibiotic treatment (yes/no)
- Days since onset of current episode of PN
- Prior treatment received for the current episode (yes/no)
- By-visit WI-NRS score at baseline
- By-visit Skin Pain NRS score at baseline
- IGA-CPG-S score at baseline
- IGA-CPG-A score at baseline
- Total BSA involvement

6.1.3. Disease History

The time since diagnosis will be summarized for all participants in the ITT Population and will be calculated as follows:

Disease duration (months) = (date of randomization – date of initial PN diagnosis + 1) / 30.4375.

6.1.4. Medical History

For participants in the ITT Population, medical history will be summarized by assigned treatment group. This summary will include the number and percentage of participants with medical history for each body system/organ class as documented on the eCRF.

6.2. Disposition of Participants

The number and percentage of participants who were randomized, who were treated, who completed the DBVC period, who discontinued treatment during the DBVC period with a primary reason for discontinuation, and who withdrew from the study during the DBVC period with a primary reason for withdrawal will be summarized for the ITT Population.

The number and percentage of participants who completed the OLE period, who discontinued treatment during the OLE period with a primary reason for discontinuation, and who withdrew from the study during the OLE period with a primary reason for withdrawal will be summarized for the OLE Safety Population.

The number of participants enrolled by country and site will also be provided by treatment group.

6.3. Protocol Deviations

For participants in the ITT Population in the DBVC period, as well as the OLE Safety Population in the OLE period, Protocol deviations recorded on the eCRF will be summarized and listed by category (critical, major, or minor) for each treatment group and overall.

6.4. Exposure

For participants in the Safety Population in the DBVC period, in the OLE Safety Population in the OLE period, and who applied ruxolitinib 1.5% cream BID throughout study participation, study cream exposure will be summarized by treatment group descriptively with duration of treatment, total amount of cream applied, and average daily application.

6.5. Study Cream Application Compliance

The overall compliance (%) for the application of ruxolitinib 1.5% cream BID or vehicle cream BID during the DBVC period will be calculated for all participants in the Safety Population as follows:

Study cream application compliance (%) = $100 \times \text{total number of nonmissing}$ applications / total number of intended applications

where

Total number of nonmissing applications = number of applications that the participant actually applied during the study

and

Total number of intended applications = $2 \times$ duration of treatment (days) – number of interrupted applications

